Potentially eligible subjects will be asked to complete the Informed Consent process, at which point the subjects will read through the IRB-approved consent form, and will meet with a research staff member who will answer any questions, explain the schedule of study procedures, and review the risks and benefits of the study. Subjects will be informed about the experimental nature, purpose, risks, and benefits of the study in accordance with procedures of the Partners IRB. There will be no time-limit placed on the consenting process. Research staff members understand that the consent is a process and not simply a matter of signing and dating the consent form. Either the PI or one of the Co-Investigators (serving as designees of the PI) will be available to help explain the study and answer questions. Once the subject consents to participate in the study, the subject will sign and date the consent form along with a member of the research staff. The subject will be provided with a copy of the consent form and the original will be stored in a secure location by a member of the study staff.

Participants will be randomly assigned to receive either ICBT or IDC. This randomization will be stratified by the following variables: (1) presence of a medication for anxiety, (2) gender, (3) type of opioid medication (agonist/partial agonist vs. antagonist), and (4) severity (defined by presence vs. absence of opioid use since initiating pharmacotherapy for opioid use).

V. STUDY PROCEDURES

All participants will receive 12 individual weekly sessions of ICBT or IDC and will complete assessments at baseline, week 12, and 1- and 3-month post-treatment follow-up visits. Breath alcohol screens will be conducted at each session and assessment visit to confirm absence of acute alcohol use. Procedures for response to a positive breathalyzer screen are specified below in Section VII. Qualitative exit interviews will be conducted at the completion of treatment. These interviews will focus on issues related to feasibility and acceptability, such as identifying the most and least helpful sessions and areas for improvement. Details of the procedures are included below.

V.1. Eligibility and Baseline Assessment

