The following procedures will be implemented to maximize study retention: (1) collection of locator information (see attached Locator Form), including multiple methods of contact for the participant (e.g., phone, email, text messaging) and at least one person who will be able to reach the participant if study staff are unable to; (2) use of mailed reminder postcards for appointments, bi-weekly check-in calls during the follow-up period, and mailed thank you notes for completed assessments; (3) use of text messaging to make contact with participants throughout the study; and, (4) provision of reimbursement for completion of study assessments (see below). These procedures are consistent with those of other longitudinal clinical trials to maximize retention (Zweben, Fucito, & O’Malley, 2009), including trials conducted within the ADATP (e.g., Weiss et al., 2009). Participants will be informed of these procedures in the consent form, including the nature of the collection of locator contacts. In the event that study staff need to contact participants’ locator (e.g. if a participant’s phone number changes), study staff will not disclose any information about the nature of the research study or the participant’s health. If participants indicate that they are comfortable communicating via text (see attached Screening Form and Locator Form), study staff will not reference the nature of the study or clinical information, and will only use text messaging as a scheduling tool for participants for whom contact by phone has not been successful, or for those who indicate that texting is their preferred method of contact. In order to maintain confidentiality, all text messages to participants will be sent through email. These strategies have yielded exceptional data completion in previous studies of integrated behavioral therapy conducted in the ADATP (e.g., > 95% main outcomes completion; Weiss et al., 2009).

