The anticipated risks associated with the proposed study are minimal. As in any study involving assessment of psychiatric symptoms, there is some risk of emotional discomfort from discussing emotional topics (e.g., symptoms of anxiety, substance use). However, this discomfort is expected to be transient. In addition, the stress reactivity tests are designed to elicit mild to moderate, transient distress. Accordingly, evidence suggests that completion of laboratory stress-reactivity paradigms is not associated with increased risk of subsequent substance use (DeSantis et al., 2009). Participants will be monitored by study staff. If a participant reports experiencing, (or study staff observes) distress at a higher level or longer duration than the mild to moderate, transient distress anticipated in study procedures, the PI will be contacted to determine whether intervention or withdrawal is indicated.

Presence of any of the following criteria throughout the study will trigger a review of the participant's appropriateness for the study by the study PI in consultation with at least one other clinical provider (either a clinician on the research team, or another member of the patient's treatment team, if a release of information has been provided): (1) any serious adverse event, (2) evidence for a significant worsening of clinical status as indicated by (a) 2 consecutive weeks of a positive urine toxicology screen (not including prescribed medications or marijuana), or (b) 2 consecutive weeks of no-showing study treatment sessions.

A core component of cognitive behavioral approaches to anxiety disorders is exposure to feared stimuli (e.g., social interactions, heights). This approach is intended to elicit moderate levels of anxiety in order for extinction of fear responding (the purported mechanism of change) to occur. Accordingly, this procedure has consistently demonstrated efficacy across the range of anxiety disorders for symptom reduction and disorder remission (e.g., Barlow et al., 2000). These

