procedures are expected to elicit moderate levels of anxiety, which are similar to the anxiety experienced by individuals with elevated anxiety symptoms in daily life. Evidence from numerous large-scale clinical trials supports the safety and tolerability of these procedures, as indicated by high retention rates (see Hembree et al., 2003) and high levels of patient satisfaction (e.g., Stein et al., 2011), including in substance-dependent samples (e.g., Mills et al., 2012; Otto et al., 2010). Nonetheless, subjects will be closely monitored for evidence of excessive or enduring distress following these procedures and precautions to protect against this risk will be taken.

Another potential risk includes the possibility that subjects may experience dangerous or suicidal behavior. These are possible because of the nature of the dually diagnosed population studied in this research. We do not anticipate that our study procedures will increase this particular risk, but there is a risk that this could occur during the study period. If a subject becomes very upset, is intoxicated, or is suicidal during the study, he or she will be seen by one of the study clinical staff members. An assessment will be conducted, and the appropriate clinical recommendation will be made; this could involve treatment either at McLean Hospital or elsewhere. If a patient provides a positive breath alcohol screen, a member of the study clinical staff will meet with the patient to determine whether he/she is able to complete the clinical or research session and to determine the participant's safety level and appropriate next steps (e.g., send to emergency room, refer to detox, send home in taxi, send home with a friend, etc.).

Accidental opioid overdose, including fatal overdose, is a possible outcome of opioid use disorder. We do not believe study procedures will increase this particular risk, because treatment enrollment has been found to be protective against overdose-related mortality among opioid-dependent individuals (Degenhardt et al., 2011). In addition, all participants are required to be on pharmacotherapy for opioid dependence which is robustly associated with a decreased risk of overdose in this population (Volkow et al., 2014). As noted above, all participants will be closely monitored and appropriate level of care will be re-evaluated if there is evidence of a worsening of clinical status.

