Tracking of Unanticipated Problems including AEs will begin at the time of consent. Unanticipated Problems including AEs will be assessed at every research assessment and treatment session (i.e., baseline, weeks 1-12, post-treatment, 1-month follow-up, and 3-month follow-up). At every study appointment, research staff will ask about any emergency room visits, inpatient admissions, etc. (see Unanticipated Event Form). In addition, participants will be closely monitored during study assessment and treatment for any psychological distress or adverse reactions to any treatment procedures and study clinicians will assess for suicidal behavior or increased severity of psychological distress. Study staff will follow the guidelines below to determine how to report and categorize Unanticipated Problems. Any AE that results in hospitalization or death will be reported to the IRB within 24 hours and will be categorized as an SAE. We will consult the IRB for guidance on any event not outlined in the protocol that are possibly related to study participation. Events that are unrelated to the disorder or study participation will not be collected in the present study given that it is a psychotherapy trial (e.g., common medical illness, such as cold or flu).

	Reporting Procedure	Data Collection Form(s)
Unanticipated problems possibly related to study participation: 
 • Unanticipated psychological stress following treatment procedures • Adverse Reactions to Physiological equipment 	Report to the PHRC IRB	Unanticipated Event Form, note as Adverse Event
Other Unanticipated Problems that are possibly related to study participation: 
 • Breaches of confidentiality 	Report to the PHRC IRB	Research progress note
Unanticipated problems related to the course of the clinical disorder being treated not related to study participation, including such examples as: 
 • Drug overdose • Suicidal ideation/suicide attempt • Increase severity of psychological distress requiring medical/psychiatric attention • Participation incarceration 	Report to PHRC IRB	Unanticipated Event Form, consult with IRB to determine whether Adverse Event or Unanticipated Problem
Hospitalization	Report to PHRC IRB	Unanticipated Event Form, consult with IRB to determine whether Adverse Event or Unanticipated Problem

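### Two of the three participant-review triggers cannot operate after week 12, and follow-up has only two scheduled event inquiries, about 8.7 weeks apart, although check-in calls already planned could close that gap

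*Combined protocol and SAP*

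**What the plan says.** Section VII (Risks and Discomforts) sets out when the PI, with at least one other clinical provider, must review whether a participant is still suitable for the study: "Presence of any of the following criteria throughout the study will trigger a review". The first criterion is any serious adverse event (SAE). The second is significant clinical worsening, shown by either (a) "2 consecutive weeks of a positive urine toxicology screen", leaving aside prescribed medications and marijuana, or (b) "2 consecutive weeks of no-showing study treatment sessions".

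Section V gives the calendar: "All participants will receive 12 individual weekly sessions of ICBT or IDC", with assessments at baseline, week 12, and 1 and 3 months after treatment. Section V.2 ties urine screens to the treatment sessions. Table 1 lists urine under the weekly column and then separately at post-treatment, 1 month and 3 months.

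Section IX.1 says that unanticipated problems, including adverse events, "will be assessed at every research assessment and treatment session (i.e., baseline, weeks 1-12, post-treatment, 1-month follow-up, and 3-month follow-up". Section V.3 lists, among the retention procedures, "bi-weekly check-in calls during the follow-up period". It does not say what is asked on these calls, and Section IX.1 does not mention them.

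Section VII also undertakes to monitor participants closely and to re-evaluate level of care on evidence of worsening. Its reassurance on overdose has two grounds. One is that "treatment enrollment has been found to be protective against overdose-related mortality". The other is that participants must be on pharmacotherapy for opioid dependence.

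**The concern.** The stated scope of the review criteria and the data they need do not match. The criteria are said to cover the whole study, but both worsening criteria rely on a weekly rhythm that belongs to the treatment phase. In follow-up the enumerated list shrinks to one item, an SAE, and that item works only once staff know of the event.

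Routine event inquiry also thins out at the point where study therapy ends and one of the two grounds for the overdose reassurance weakens. Section VII itself names fatal overdose and suicidal behavior as possible in this population. What is at stake is timely knowledge of such events between the 1- and 3-month visits, and whether the protocol delivers the monitoring it describes. The trial's efficacy estimates are not affected.

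**Working it through.** The plan states no figure for the interval between event inquiries, so there is none to reproduce. What follows is calendar arithmetic from the visit schedule, with 1 month = 4.35 weeks.

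**Visit times, counted from the start of treatment**
- Post-treatment: week 12 (Section V).
- 1-month follow-up: 12 + 4.35 = 16.35, about week 16.3.
- 3-month follow-up: 12 + 3 × 4.35 = 25.05, about week 25.

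**Can criterion (a), consecutive weekly positive urine, be met in follow-up?** After post-treatment, Table 1 has screens at about weeks 16.3 and 25. The spacings are 4.35 weeks and 2 × 4.35 = 8.7 weeks, so two screens never fall in consecutive weeks. There is one edge case: if the post-treatment visit falls in the week after session 12, positive screens at both could satisfy (a) once, just as treatment ends. Section V.4.4 mentions weekly urine without an end date. I read it with Section V.2 and Table 1, which place weekly collection at sessions and list the follow-up screens separately. Section V.3 also allows follow-up assessments by phone, with fewer data points collected.

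**Can criterion (b), missed sessions, be met in follow-up?** No. After 12 weekly sessions there are none left to miss.

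**How much of the study is this?**
- Treatment lasts 12 / 4.35 = 2.76 months, so treatment plus follow-up is about 5.8 months. Follow-up is 3 / 5.76 = 52%.
- Section VI speaks of 7 months of participation. On that figure the share is 3 / 7 = 43%.

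**Event inquiries listed in Section IX.1**
- Full attender: 1 (baseline) + 12 (sessions) + 1 (post-treatment) + 2 (follow-up) = 16.
- Only 2 of the 16 come after the post-treatment visit.
- Longest interval in follow-up: 8.7 weeks, or 8.7 × 7 = 61 days. During treatment the interval is 1 week.

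**What the planned calls could add**
- Every two weeks: 13.05 / 2 = 6.5, so about 6 calls over follow-up. Between the 1- and 3-month visits, 8.7 / 2 = 4.35, so about 4.
- If each call included the event questions, the longest interval between inquiries would be about 2 weeks.
- If the calls are meant to be twice a week, the interval would be 3 to 4 days. The plan does not say which is meant.

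**The case against.** The strongest reply is that contact does not stop at week 12. The check-in calls keep the longest planned interval without contact at about 2 weeks. The SAE criterion stays active, and Section IX.1 treats any adverse event leading to hospitalization or death as an SAE. Section VII says clinical staff will see anyone who becomes very upset, intoxicated or suicidal during the study, and Section IX commits the PI to continuous safety monitoring for its duration. Neither is limited to the treatment phase. The Timeline Follow-Back at 1 and 3 months recovers substance use between visits. Finally, the Section VII review concerns suitability for the study, which matters less once study treatment is over.

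Much of this stands, and it rules out several stronger readings that a reader might infer:

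- *That events go unseen for about two months.* The 8.7 weeks separate scheduled event inquiries, not contacts. Staff may learn of an event on a call or by spontaneous report, and the next visit can capture it late.
- *That only an SAE can prompt any clinical response in follow-up.* This is true of the enumerated list, but not of the general commitments in Sections VII and IX.
- *That nothing happens for someone who stops attending until week 12.* Criterion (b) triggers a review after two missed weeks, and Section VI plans vigorous outreach to people who leave treatment.
- *That event counts by arm would not be comparable.* Section VI plans no between-arm comparison of events, and the documents give no figure for differential attendance.

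The reply does not remove the core. The calls appear only as a retention measure, with no stated safety questions and no link to the Unanticipated Event Form or the Section VII review. The SAE criterion depends on staff learning of the event. For overdose and suicidal ideation or attempt, the Section IX.1 table asks for consultation with the IRB on how to classify them, and relapse is not among its examples. An overdose without hospitalization, or a relapse, might therefore meet no enumerated criterion in follow-up even if staff heard of it.

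**Conclusion.** The point holds as a mismatch within the protocol and a gap in scheduled inquiry. Apart from the edge case at the post-treatment visit, both worsening criteria are inoperative for the 3 months of follow-up (43% to 52% of study time, depending on which duration is used). Only the SAE criterion remains of the enumerated list. Scheduled event inquiry falls from weekly to two occasions, with a longest interval of about 8.7 weeks. The likely consequence is delayed knowledge of some events rather than their loss.

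This rests on three assumptions: weekly urine collection ends with the sessions, as Section V.2 and Table 1 indicate; the list in Section IX.1 is complete, as its wording suggests; and the calls have no safety content beyond what Section V.3 states. If a call script or the event form already provides for these questions, only the wording needs to be reconciled. The change is worth making because the contacts are already planned.

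**What to change.** In Section IX.1, add the follow-up check-in calls of Section V.3 to the contacts at which the Unanticipated Event Form is completed, and state the call frequency, since the present term can mean every two weeks or twice a week. At every two weeks, the longest interval between event inquiries falls from about 8.7 to about 2 weeks.

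Reconcile Sections V.3, VII and IX.1: say which Section VII criteria apply after week 12, and whether information from a call can lead to the Section VII review. Whether any further clinical criterion is needed in follow-up, and what it should be, is for the sponsor to decide.

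The cost is a protocol amendment, a few more minutes on each call, and slightly more events to report. With 54 participants and about 6 calls each, this covers at most 54 × 6 = 324 calls, all already planned. No visits are added. Section IX.1 assigns the assessment of suicidal behavior to study clinicians, so the amendment should say how a concern raised on a call reaches them.

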**PARTNERS HUMAN RESEARCH COMMITTEE
DETAILED PROTOCOL**

PRINCIPAL/OVERALL INVESTIGATOR

R. [name].

PROTOCOL TITLE

Randomized Controlled Trial of Cognitive Behavioral Therapy for Anxiety and Opioid Dependence

FUNDING

National Institute on Drug Abuse (K23 DA035297, K23 DA 035297-04S1)

InfoEd Link: 2013D001549

VERSION DATE

November 30, 2018

I. BACKGROUND AND SIGNIFICANCE

Opioid dependence and anxiety disorders frequently co-occur, with over 60% of opioid-dependent individuals meeting criteria for a lifetime anxiety disorder (Conway et al., 2006). Individuals with anxiety disorders are more likely to use opioids (Sareen et al., 2006) and have higher incident risk for opioid dependence (Martins et al., 2009). Anxiety symptoms often precede opioid use (Ouimette et al., 2010), with anxiety reduction among the most commonly reported motives for opioid use (Rigg et al., 2010). The co-occurrence of opioid dependence and anxiety disorders is associated with lower quality of life (Carpentier et al., 2009) as well as poor treatment retention (Lejuez et al., 2008) and worse drug use and anxiety outcomes (e.g., Compton et al., 2003; Lavie et al., 2009). However, there has been a paucity of research on treatment for co-occurring opioid dependence and anxiety disorders. Clinical trials testing behavioral treatments for anxiety disorders have consistently excluded participants with substance dependence (e.g., Barlow et al., 2000), and there are no published large-scale pharmacotherapy trials for this population. Few studies have examined integrated behavioral treatments for co-occurring substance dependence and anxiety disorders, with most focused specifically on posttraumatic stress disorder (PTSD; Hien et al., 2009; Mills et al., 2012), and one study of obsessive-compulsive disorder (OCD; Fals-Stewart et al., 1992). For other anxiety disorders, which are present in 60% of opioid-dependent individuals and are the focus of the current application, published research has focused on alcohol dependence (Hesse, 2009), with no published studies to date for opioid dependence. Thus, research on optimal treatment approaches is needed to improve outcomes for this population.

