Participants will be fully informed of the nature of the risks involved during the informed consent process and will have the ability to discontinue and withdraw consent at any time. All study personnel will be trained in the appropriate care of human participants, and will have completed the National Cancer Institute (NCI) course, Human Participants Protections Education for Research Teams, and research assistants will be closely supervised by the study PI. As part of the informed consent process, participants will be informed that if they feel uncomfortable responding to any question that they are free to choose not to respond or to express their discomfort. Each participant will be made aware that participation is completely voluntary and that he or she may withdraw participation at any time without penalty.

VIII. POTENTIAL BENEFITS

The major potential benefit to participants is the receipt of treatment that might help them to achieve their goals of maintaining abstinence from opioids and reducing anxiety. Participants will receive free cognitive behavioral treatment as part of this study from providers experienced in treating substance dependence. Participants also will receive the potential benefit of participating in a study that may contribute to establishing more effective treatment for patients with co-occurring opioid dependence and anxiety disorders. Given the minimal risks associated with the proposed investigation, we believe that this is a very acceptable risk-benefit ratio.

IX. MONITORING AND QUALITY ASSURANCE

The PI will have responsibility for continuous monitoring of the data and safety of subjects in the study. Further consultation will be obtained if necessary from the McLean Hospital Office of Research Administration.

Continuous, close monitoring of safety issues by the PI will take place throughout the study's duration with prompt reporting of adverse events to the Partners IRB. At the time of annual, continuing review we will provide the Partners IRB with a summary of any unexpected and related adverse events as well as any other unanticipated problems that occurred since the last continuing review. We will also follow the Partners IRB policies for expedited reporting of Adverse Events and Serious Adverse Events.

IX.1. Reporting Unanticipated Problems Including Adverse Events (AEs) and Serious Adverse Events (SAEs)

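### The reporting table files overdose, suicidality and severe distress as unrelated to participation by event type, with no per-event relatedness judgement and no rule for events that also fit the possibly related row

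*Combined protocol and SAP*

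**What the plan says.** Section IX.1 introduces the reporting table with "Study staff will follow the guidelines below to determine how to report and categorize Unanticipated Problems". Three features of the table matter here.

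- **First row.** Problems possibly related to participation. The examples include "Unanticipated psychological stress following treatment procedures". These are reported to the IRB, entered on the Unanticipated Event Form and noted as an Adverse Event.
- **Third row.** Headed "Unanticipated problems related to the course of the clinical disorder being treated not related to study participation, including such examples as". The examples are drug overdose, "Suicidal ideation/suicide attempt", "Increase severity of psychological distress requiring medical/psychiatric attention" and incarceration. These are also reported to the IRB on the same form. The IRB is then consulted on whether each is an Adverse Event or an Unanticipated Problem.
- **Hospitalization and death.** Each has its own row, without any statement on relatedness.

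Section IX promises the IRB, at annual review, "a summary of any unexpected and related adverse events" together with other unanticipated problems since the last review.

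On the treatment, Section VII describes exposure as a core part of cognitive behavioral approaches to anxiety disorders: "This approach is intended to elicit moderate levels of anxiety in order for extinction of fear responding". On the disorder, Section I states "Anxiety symptoms often precede opioid use" and adds that reducing anxiety is among the most common reported motives for opioid use.

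**The concern.** Whether an event is related to study treatment is a judgement about that event. The third row instead attaches the answer to a type of event, and the types include overdose and suicidality, two risks that Section VII itself singles out. One arm receives a treatment that, going by Section VII, deliberately provokes anxiety in people for whom the protocol says anxiety often comes before opioid use. A link between treatment and these events may be unlikely, but it is not implausible on the protocol's own account.

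At stake is what the trial can say about harm. Section VI describes this as a Stage 1 study whose results inform a larger Stage 2 trial. A statement that no serious event was related to treatment would carry little weight if it rested on a heading chosen in advance and not on an assessment of each event.

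**Working it through.** No arithmetic applies. The check sets the safety passages side by side.

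1. **Is the table binding?** Yes. Section IX.1 makes it the guide for both reporting and categorizing, so its headings have consequences.

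2. **Does any passage provide a relatedness judgement for third-row events?** Three passages come close.
   - The IRB consultation attached to the row asks whether the event is an Adverse Event or an Unanticipated Problem. Relatedness is not the stated question.
   - Section IX.1 also offers IRB guidance on possibly related events, but only for events that the protocol does not outline. Overdose, suicidality and severe distress are outlined, so this route does not cover them.
   - Section VII has the principal investigator and another clinical provider review a participant after a serious adverse event or a marked worsening. That review concerns whether the participant is still appropriate for the study, not what caused the event.

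   No assessor, criteria or step for judging cause is described.

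3. **Do the rows exclude one another?** Take a participant whose distress after an exposure session goes beyond what was expected and leads to psychiatric attention.
   - By timing, this is unanticipated stress after a treatment procedure: first row, possibly related, Adverse Event.
   - By severity, it is increased distress needing psychiatric attention: third row, not related, Adverse Event status left to consultation.

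   Both descriptions fit and there is no tie-break. Two staff members could each follow the table and record opposite labels.

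4. **Is unrelatedness safe to presume?** Put the Section VII statement on eliciting anxiety next to the Section I statement that anxiety often precedes opioid use. Together they give a plausible path from treatment-elicited anxiety to opioid use. Section VII also says the team does not expect its procedures to raise suicidal or overdose risk. That is a reasonable prior belief, but not a finding about any particular event.

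5. **Where does the label have an effect?**
   - In the annual summary, a third-row event that consultation classes as an Adverse Event, but that carries the heading's label, does not meet the related-events part. It has to enter through the part for other unanticipated problems.
   - In the analysis, Section VI plans no comparison of adverse events by arm, so no planned output would show an imbalance that the labels had missed.

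**The case against.** The strongest reply is that the table sorts events by cause. On that reading the third-row heading is conditional: it covers these events when they are due to the disorder, and does not declare every overdose or suicide attempt unrelated. The reading is fair. It does not close the gap, because nobody is assigned to decide whether the condition is met.

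Three stronger conclusions are tempting, and the documents do not support them.

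- **That harm from ICBT would necessarily be labelled unrelated.** The conditional reading is open, and the first row exists for reactions to treatment procedures. The text shows that mislabelling could happen, not that it would.
- **That the same reaction counts as related when mild and unrelated when severe.** The first row has no severity limit, so severe distress after a procedure can properly be placed there. The defect is overlap without a tie-break.
- **That serious events would be kept from the IRB, or that no serious harm could ever be called related.** Every row is reported to the IRB. The third row is itself headed as unanticipated problems, which the annual summary includes. A fatal overdose, or one leading to hospitalization, also fits a row with no relatedness label. Adverse events that result in hospitalization or death go to the IRB within 24 hours as serious, although the rows for those two outcomes leave Adverse Event status to consultation; that separate mismatch should be reconciled.

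Two further points stand. The Unanticipated Event Form and the IRB's policies are not among the documents, so the form may already have a relatedness field. And the label does not prevent a comparison by arm, since the events are recorded either way; such a comparison is simply not planned.

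**Conclusion.** The concern holds as a gap in attribution and in comparison between arms. The operative table groups overdose, suicidality and severe distress under a heading of unrelatedness, no per-event judgement is described, and severe distress after a treatment procedure falls in two rows with opposite labels. Treatment-related harm could therefore be recorded as unrelated.

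The size cannot be expressed in numbers, because the documents give no event rates. What can be stated is the scope: three of the four examples in the third row are serious clinical events for which cause matters, and one of them overlaps directly with the first row. The change should be made, but this is a gap in classification, not a failure of reporting.

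The conclusion rests on two assumptions. The first is that ICBT includes the exposure work described in Section VII; the session overview that Section V.2 places in an appendix is not in the available text. The second is that no relatedness assessment is specified in the form or the IRB policies. If one is, the missing judgement is largely met, but the heading and the overlap still need correcting.

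**What to change.** Make four changes, none of which alters clinical management.

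1. In the third-row heading, delete the five words that declare the events unrelated to participation. The row then describes events in the course of the disorder without ruling on cause.
2. Record a relatedness judgement for each event on the Unanticipated Event Form, if it has no such field already, made by the existing investigators. Using someone other than the participant's study therapist would be good practice, but the point does not depend on it.
3. State that distress following a treatment procedure is reported under the first row at any severity.
4. Add to Section VI a descriptive table by arm of overdoses, suicidal events, hospitalizations and deaths, regardless of relatedness.

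The cost is a wording change, at most one field on an existing form, and one descriptive table. No extra visits or staff are needed. With a target of 54 participants the table should be read as description, not as a test.
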